## 10.1.3. Events that Require Expedited Reporting to Sponsor

The following events also require reporting to the sponsor (or designee) within 24 hours of learning of the event:

- SAEs.
- **AESIs**; serious and nonserious: Adverse events of special interest for this study include the following:
  - Anaphylactic reactions
  - Systemic hypersensitivity reactions
  - Helminthic infections
  - Any severe type of conjunctivitis or blepharitis
  - Keratitis
  - Clinically symptomatic eosinophilia (or eosinophilia associated with clinical symptoms)
- **Pregnancy:** Although pregnancy is not considered an AE, it is the responsibility of the investigator to report to the sponsor (or designee), within 24 hours of identification, any pregnancy occurring in a female, during the study or within 12 weeks of the last dose of study drug. Any complication of pregnancy affecting a female study patient and/or fetus and/or newborn that meets the SAE criteria must be reported as an SAE. Outcome for all pregnancies should be reported to the sponsor.

# **10.2. Definitions**

## 10.2.1. Adverse Event

An AE is any untoward medical occurrence in a patient administered a study drug which may or may not have a causal relationship with the study drug. Therefore, an AE is any unfavorable and unintended sign (including abnormal laboratory finding), symptom, or disease which is temporally associated with the use of a study drug, whether or not considered related to the study drug (ICH E2A Guideline. Clinical Safety Data Management: Definitions and Standards for Expedited Reporting, Oct 1994).

#### 10.2.2. Serious Adverse Event

An SAE is any untoward medical occurrence that at any dose:

- Results in **death** includes all deaths, even those that appear to be completely unrelated to study drug (eg, a car accident in which a patient is a passenger).
- Is **life-threatening** in the view of the investigator, the patient is at immediate risk of death at the time of the event. This does not include an AE that had it occurred in a more severe form, might have caused death.
- Requires in-patient **hospitalization** or **prolongation of existing hospitalization**. In-patient hospitalization is defined as a hospital admission (any duration) or an emergency room visit for longer than 24 hours. Prolongation of existing hospitalization is defined as a hospital stay that is longer than was originally anticipated for the event, or is prolonged due to the development of a new AE as determined by the investigator or treating physician.
- Results in persistent or significant **disability/incapacity** (substantial disruption of one's ability to conduct normal life functions).
- Is a congenital anomaly/birth defect
- Is an **important medical event**. Important medical events may not be immediately lifethreatening or result in death or hospitalization, but may jeopardize the patient or may require intervention to prevent one of the other serious outcomes listed above (eg, intensive treatment in an emergency room or at home for allergic bronchospasm; blood dyscrasias or convulsions that do not result in hospitalization; or development of drug dependency or drug abuse).

Criteria for reporting SAEs must be followed for these events.

#### **10.2.3.** Adverse Events of Special Interest

An AESI (serious or non-serious) is one of scientific and medical interest specific to the sponsor's product or program, for which ongoing monitoring and rapid communication by the investigator to the sponsor can be appropriate. Such an event might warrant further investigation in order to characterize and understand it. For a list of AESIs, see Section 10.1.3.

## 10.2.4. Severity

The severity of AEs will be graded according to the following scale:

**Mild:** Does not interfere in a significant manner with the patient's normal functioning level. It may be an annoyance. Prescription drugs are not ordinarily needed for relief of symptoms, but may be given because of personality of the patient.

**Moderate:** Produces some impairment of functioning but is not hazardous to health. It is uncomfortable or an embarrassment. Treatment for symptom may be needed.

**Severe:** Produces significant impairment of functioning or incapacitation and is a definite hazard to the patient's health. Treatment for symptom may be given and/or patient hospitalized.

If a laboratory value is considered an AE, its severity should be based on the degree of physiological impairment the value indicates.

#### Injection Site Reactions

The severity of injection site reactions will be graded according to the following scale (semi-colon indicates "or" within description of grade):

**Mild**: Pain that does not interfere with activity; mild discomfort to touch; <5 cm of erythema or induration that does not interfere with activity

**Moderate**: Pain that requires repeated use of non-narcotic pain reliever >24 hours or interferes with activity; discomfort with movement; 5.1 cm to 10 cm erythema or induration or induration that interferes with activity

**Severe**: Pain that requires any use of narcotic pain reliever or that prevents daily activity; significant discomfort at rest; >10 cm erythema or induration; prevents daily activity; requires emergency room visit or hospitalization; necrosis or exfoliative dermatitis

## 10.2.5. Causality

The investigator must provide causality assessment as to whether or not there is a reasonable possibility that the drug caused the adverse event, based on evidence or facts, his/her clinical judgment, and the following definitions. The causality assessment must be made based on the available information and can be updated as new information becomes available.

For double-blinded studies using an active comparator, the investigator should consider all study drugs in determining event causality.

The following factors should be considered when assessing causality:

- Temporal relationship: time to onset versus time drug was administered
- Nature of the reactions: immediate versus long term
- Clinical and pathological features of the events
- Existing information about the drug and same class of drugs
- Concomitant medications
- Underlying and concurrent illnesses

REGENERON CONFIDENTIAL Page 75 of 99

- Response to dechallenge (drug discontinuation) or dose reduction, if applicable
- Response to rechallenge (re-introduction of the drug) or dose increase, if applicable
- Patient's medical and social history

Causality to the study drug (including study drug administration):

- Related:
  - The AE follows a reasonable temporal sequence from study drug administration, and cannot be reasonably explained by the nature of the reaction, patient's clinical state (eg, disease under study, concurrent diseases, concomitant medications), or other external factors.
  - or
  - The AE follows a reasonable temporal sequence from study drug administration, and is a known reaction to the drug under study or its class of drugs, or is predicted by known pharmacology.
- Not Related:
  - The AE does not follow a reasonable sequence from study drug administration, or can be reasonably explained by the nature of the reaction, patient's clinical state (eg, disease under study, concurrent diseases, and concomitant medications) or other external factors.

Causality to the study conduct (protocol-specified procedure):

- Related:
  - The AE follows a reasonable temporal sequence from a protocol-specified procedure, and cannot be reasonably explained by the nature of the reaction, patient's clinical state (eg, disease under study, concurrent diseases, and concomitant medications), or other external factors.
- Not Related:
  - The AE does not follow a reasonable sequence from a protocol-specified procedure, or can be reasonably explained by the nature of the reaction, patient's clinical state (eg, disease under study, concurrent diseases, and concomitant medications) or other external factors.

# **10.3.** Safety Monitoring

The investigator will monitor the safety of study patient at his/her site(s) as per the requirements of this protocol and consistent with current Good Clinical Practice (GCP). Any questions or concerns should be discussed with the sponsor in a timely fashion. The sponsor will monitor the safety data from across all study sites. The medical/study director will have primary responsibility for the emerging safety profile of the compound, but will be supported by other departments (eg, Pharmacovigilance; Risk Management; Biostatistics and Data Management). Safety monitoring will be performed on an ongoing basis (eg, individual review of SAEs) and on a periodic, cumulative aggregate basis.

REGENERON CONFIDENTIAL Page 76 of 99

# 10.4. Notifying Health Authorities, Institutional Review Board/Ethics Committee, and Investigators

During the study, the sponsor and/or the CRO will inform health authorities, ECs or institutional review boards (IRBs), and the participating investigators of any SUSARs (suspected unexpected serious adverse reactions) occurring in other study centers or other studies of the active study drug (REGN668; dupilumab), as appropriate per local reporting requirements. In addition, the sponsor and/or CRO will comply with any additional local safety reporting requirements. All notifications to investigators will contain only blinded information.

Upon receipt of the sponsor's notification of a SUSAR that occurred with the study drug, the investigator will inform the IRB/EC unless delegated to the sponsor.

Event expectedness for study drug (dupilumab) is assessed against the Reference Safety Information section of the current Investigator's Brochure that is effective for expedited safety reporting.

At the completion of the study, the sponsor will report all safety observations made during the conduct of the trial in the CSR to health authorities and ECs/IRBs as appropriate.

# 11. STATISTICAL PLAN

This section provides the basis for the SAP for the study. The SAP will be revised prior to the end of the study to accommodate amendments to the clinical study protocol and to make changes to adapt to unexpected issues in study execution and data that may affect the planned analyses. The final SAP will be issued before the first database lock.

Endpoints are listed in Section 4. Analysis variables are listed in Section 5.

Data collected through the implementation of new CRFs regarding the impact of the COVID-19 pandemic on patients will be summarized (eg, discontinuation due to COVID-19). Any additional analyses and methods required to investigate the impact of COVID-19 on the efficacy (eg, missing data due to COVID-19) and safety evaluation will be specified in the SAP.

# **11.1.** Statistical Hypothesis

The primary analyses of the study compare the treatment effect of dupilumab 300 mg Q2W against placebo on the absolute change from baseline in pre-bronchodilator FEV1.

The statistical hypotheses to test dupilumab 300 mg Q2W against placebo on having a greater increase from baseline in pre-bronchodilator FEV1 at week 24 are as follows:

- Null hypothesis:  $\Delta_{\text{Dupilumab}} \Delta_{\text{Pbo}} = 0$
- Alternative hypothesis:  $\Delta_{\text{Dupilumab}} \Delta_{\text{Pbo}} \neq 0$

where  $\Delta_{\text{Dupilumab}}$  and  $\Delta_{\text{Pbo}}$  represent the absolute change from baseline in pre-bronchodilator FEV1 at week 24 in the dupilumab and placebo groups, respectively.

# **11.2.** Justification of Sample Size

The power calculation for this study is based on a comparison between dupilumab 300 mg Q2W and placebo with regard to the primary efficacy endpoint of the absolute change from baseline in pre-bronchodilator FEV1 at week 24. Assuming a 1:1 randomization ratio, a standard deviation (SD) for the change from baseline in pre-bronchodilator FEV1 at week 24 of **SEC** in both groups, a 2-sided Type 1 error of 0.05, and a dropout rate of **SEC** by week 24, with approximately 60 randomized patients (~30 patients per group), the study will have approximately 96% power to detect a difference of **SEC** in the change from baseline in pre-bronchodilator FEV1 at week 24 between the dupilumab and placebo groups, based on the 2-sample t-test.

# 11.3. Analysis Sets

## 11.3.1. Efficacy Analysis Sets

The full analysis set (FAS) includes all randomized patients. It is based on the treatment allocated (as randomized), regardless of whether the treatment kit was used or not. Efficacy endpoints will be analyzed using the FAS.

## 11.3.2. Safety Analysis Set

The safety analysis set (SAF) includes all randomized patients who received any study drug; it is based on the treatment received (as treated). Treatment compliance/administration and all clinical safety variables will be analyzed using the SAF.

## 11.3.3. Pharmacokinetic Analysis Sets

The PK analysis population includes all patients who received any study drug and who had at least 1 non-missing drug concentration result following the first dose of study drug.

## 11.3.4. Immunogenicity Analysis Sets

The ADA analysis set includes all patients who received any study drug and who had at least 1 non-missing ADA result following the first study dose.

The NAb analysis set includes all patients who received any study drug and who are negative in the ADA assay or with at least 1 non-missing result in the NAb assay (patients who are ADA-negative are set to negative in the NAb analysis set).

# **11.4.** Statistical Methods

For continuous variables, descriptive statistics will include the following information: the number of patients reflected in the calculation (n), mean, standard deviation, Q1, median, Q3, minimum, and maximum.

For categorical data, frequencies and percentages will be displayed for each category.

## **11.4.1. Patient Disposition**

The following will be provided:

- The total number of screened patients: met the inclusion criteria regarding the target indication and signed the ICF
- The total number of randomized patients: received a randomization number
- The total number of patients who discontinued the study, and the reasons for discontinuation
- The total number of patients who discontinued from study treatment, and the reasons for discontinuation
- A listing of patients treated but not randomized, patients randomized but not treated, and patients randomized but not treated as randomized
- A listing of patients prematurely discontinued from treatment, along with reasons for discontinuation

## **11.4.2.** Demography and Baseline Characteristics

Demographic and baseline characteristics will be summarized descriptively by treatment group, and by all patients combined.

REGENERON CONFIDENTIAL Page 79 of 99

## 11.4.3. Primary Efficacy Analysis

The absolute change from baseline in pre-bronchodilator FEV1 at week 24 will be analyzed using a mixed-effects model with repeated measures (MMRM) approach. The vector of responses will consist of the absolute change from baseline in pre-bronchodilator FEV1 at weeks 2, 4, 8, 12, and 24. For patients who discontinue study treatment prior to week 24, any off-study treatment prebronchodilator FEV1 values collected after the discontinuation of study treatment through week 24 will be included in the analysis. The MMRM model will include OCS use at screening, OAF use at screening, region, age, sex, height, baseline eosinophil count, treatment, visit, treatment-byvisit interaction, baseline pre-bronchodilator FEV1 value, and baseline pre-bronchodilator FEV1 value-by-visit interaction as covariates. An unstructured covariance matrix will be used to model the correlations between repeated measurements. Parameters will be estimated using the restricted maximum likelihood (REML) method and the Newton-Raphson algorithm. Statistical inference for the treatment comparison of the absolute change from baseline in pre-bronchodilator FEV1 at week 24 will be derived from the MMRM model using the Kenward Roger method for calculation of the denominator degrees of freedom for the tests of the fixed effects. If the model does not converge, alternative model specifications (eg, a different covariance structure or reduction in the number of covariates) will be applied; details will be provided in the SAP.

Primary Efficacy Endpoint	Intercurrent event(s) handling	Missing data handling	
	strategies	approaches	
Change from baseline in pre-bronchodilator FEV1 at week 24	
 
strategies
 
The intercurrent events will be handled using the treatment policy strategy as follows: 
 
Taking rescue medications with systemic corticosteroids and/or oral antifungal drugs (including an increase in dose) for asthma or ABPA for any reason: all endpoint data collected after use of rescue medication will be used in the analysis
 
Taking prohibited medications: all endpoint data will be included in the analysis irrespective of use of prohibited medications
 
Discontinuing the study treatment: all endpoint data collected after discontinuation will be used in the analysis
 
 
 
	approaches Two types of missing data: 1) Patients discontinuing from the study prior to the analysis time point (week 24) will have missing data from the time of discontinuation through week 24; 2) Some intermittently missing data are expected because of occasionally missing a study visit while continuing with the randomized treatment Missing data handling: for both types of missing data, the primary analysis MMRM model assumes that missing data are MAR, that is, that patients with missing data would have efficacy outcomes like those in similar patients in their treatment group who continue their randomized treatment through the time point at which data are	
	anary 515	randomized treatment through the time point at which data are missing	

For the primary estimand of interest for the primary endpoint, the intercurrent events, strategies, and the corresponding missing data handling approaches are provided as below:

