7.2.1.1. Estimand Framework

For the primary efficacy endpoint of the absolute change from baseline in pre-bronchodilator FEV1 at Week 24, intercurrent events may arise as a result of:

- i. Taking rescue medications with systemic corticosteroids and/or oral antifungal therapies (including an increase in dose) for asthma or ABPA for any reason
- ii. Taking prohibited medications
- iii. Discontinuing the study treatment

[figure not shown]
These intercurrent events will be handled using the treatment policy strategy as follows:

[figure not shown]
- i. All endpoint data collected after the use of rescue medication through Week 24 will be used in the analysis
- ii. All endpoint data through Week 24 will be included in the analysis irrespective of the use of prohibited medications
- iii. All endpoint data collected after treatment discontinuation through Week 24 will be used in the analysis

There are two ways in which missing data may arise: (i) patients who discontinue from the study prior to Week 24 will have (monotone) missing data from the last contact date through Week 24 and (ii) some intermittently missing data are expected due to patients occasionally missing a study visit or failure to obtain valid spirometry measurements at the study visit. For both types of missing data, the MMRM analysis model assumes that missing data are missing at random (MAR), that is, that patients with missing data at a given time point would have outcomes similar to those of patients in their treatment group with observed data at the given time point.

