7.2.1.2. Sensitivity/Supplemental Analyses

[figure not shown]
A tipping point analysis will be performed as a sensitivity analysis of the primary efficacy endpoint of the absolute change from baseline in pre-bronchodilator FEV1 at Week 24 (provided that the results of the primary analysis described in Section 7.2.1 is statistically significant). The tipping point analysis will be implemented via a pattern-mixture model-multiple imputation approach as described in the steps below:

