14. APPENDIX

14.1. Summary of Statistical Analyses

Efficacy/PD Analysis:

Endpoint	Analysis Population	Primary Analysis	Statistical Method	Other Analyses
Primary Endpoint				
Pre-bronchodilator FEV1	FAS	Absolute change from baseline at Week 24	MMRM with OCS use at screening, OAF use at screening, region, age at screening, sex, height at screening, baseline eosinophil count, treatment, visit, treatment-by-visit interaction, baseline pre-bronchodilator FEV1 value, and baseline pre-bronchodilator FEV1 value-by-visit interaction as covariates and unstructured covariance matrix	Tipping point analysis implemented via a pattern-mixture model-multiple imputation approach
Secondary Endpoints				
Severe respiratory exacerbations	FAS	Annualized rate of severe respiratory exacerbations over the 24-52-week treatment period	Negative binomial regression with OCS use at screening, OAF use at screening, region, number of severe respiratory exacerbations in the 12 months prior to the screening visit, baseline eosinophil count, and treatment as covariates	
	FAS	Annualized rate of ABPA-related exacerbations over the 24-52-week treatment period	Negative binomial regression with OCS use at screening, OAF use at screening, region, number of severe respiratory exacerbations in the 12 months prior to the screening visit, baseline eosinophil count, and treatment as covariates	
	FAS	Annualized rate of severe respiratory exacerbations requiring either hospitalization or observation for >24 hours in an ED/urgent care facility over the 24-52-week treatment period	Negative binomial regression with OCS use at screening, OAF use at screening, region, number of severe respiratory exacerbations in the 12 months prior to the screening visit, baseline eosinophil count, and treatment as covariates	

Endpoint	Analysis Population	Primary Analysis	Statistical Method	Other Analyses
ACQ-5 score	FAS [†]	Absolute change from baseline in the ACQ-5 score at each time point at which the ACQ-5 is administered during the 24-52-week treatment period	t-distribution	
SGRQ total score	FAS [†]	Absolute change from baseline in the SGRQ total score at each time point at which the SGRQ is administered during the 24-52-week treatment period	t-distribution	
	FAS [†] population with baseline SGRQ total score ≥ 4 points	Proportion of participants who achieve a reduction in the SGRQ total score of ≥ 4 points from baseline at Weeks 12, 24, 36, and 52	Wilson score confidence limits	

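### The estimand is treatment policy, but missing Week 24 FEV1 of study leavers is inferred mostly from on-drug patients, and no listed analysis gives an estimate under an off-drug assumption

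*Protocol*

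**What the plan says.** Both documents apply treatment policy to three intercurrent events: rescue medication, prohibited medication and stopping study drug. For the last, SAP 7.2.1.1 states: "All endpoint data collected after treatment discontinuation through Week 24 will be used in the analysis". The primary model (protocol 11.4.3, SAP 7.2.1) is an MMRM for change in pre-bronchodilator FEV1 at Weeks 2, 4, 8, 12 and 24. It has treatment, visit, their interaction and baseline covariates, but no term for whether a patient is on or off drug at a visit.

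Missing values are taken as MAR, whether they arise from leaving the study or from a skipped visit. The two documents explain this differently. Protocol 11.4.3 says it means "that patients with missing data would have efficacy outcomes like those in similar patients in their treatment group who continue their randomized treatment". SAP 7.2.1.1 compares with same-arm patients who have a value at that time point and does not mention continued treatment.

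Protocol 11.4.3 leaves sensitivity analyses optional and defers the details to the SAP. SAP 7.2.1.2 commits to a tipping point analysis, "provided that the results of the primary analysis described in Section 7.2.1 is statistically significant". In the legible primary-endpoint row of SAP 14.1 the only other analysis is: "Tipping point analysis implemented via a pattern-mixture model-multiple imputation approach".

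**The concern.** Under treatment policy the target is the Week 24 FEV1 of everyone randomized, including those who have stopped the drug. Leaving the study ends study dosing, so the unobserved values of leavers are values off study drug. The model fills that gap from whoever is observed in the same arm, and most of those patients are still being dosed. If benefit fades after stopping, the dupilumab mean is too high and the placebo mean has no matching error. The result would be reported as a treatment-policy effect while being partly an on-drug effect, in the trial's only tested hypothesis. With about 30 patients per arm, three dupilumab leavers are already 10%.

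The protocol also pulls in two directions on how much off-drug data will exist. Section 8.4.2 encourages patients who stop study drug to remain in the study. Section 8.4.2.2 says that missing more than 4 consecutive doses leads to discontinuation from the study. Read literally, the second removes data that the estimand needs.

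**Working it through.** **1. The plan's own figure.** Protocol 11.2 gives these inputs: "Assuming a 1:1 randomization ratio", "a 2-sided Type 1 error of 0.05", "approximately 60 randomized patients (~30 patients per group", and "the study will have approximately 96% power" from a two-sample t-test. SD, planned difference and dropout are blacked out, so the 96% cannot be reproduced. Solving it backwards with the noncentral t gives the difference/SD that it implies: 0.97 with 30 per arm, 1.01 with 28 (5% dropout), 1.03 with 27 (10%), 1.05 with 26 (15%) and 1.09 with 24 (20%). The stated power is possible but unverifiable.

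**2. Bias formulas.** Let D be the on-drug effect, m the share of the dupilumab arm missing at Week 24, r the share off drug but observed, and f the fraction of D kept off drug.

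- Treatment-policy effect: (1−m−r)D + (m+r)fD
- MAR as the protocol words it: (1−r)D + rfD
- MAR as the SAP words it: [(1−m−r)D + rfD]/(1−m)

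**3. Size with r = 0.** Both MAR versions then equal D, and the overstatement is m(1−f)/[1−m(1−f)]. D = 0.26 L is an assumption. It is the post-hoc subgroup result from 30 patients in protocol 3.3.1 and is not stated to be the planning effect. The shares missing are assumed too.

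| Missing at Week 24 | Treatment-policy effect, f = 0 | Overstatement, f = 0 | Treatment-policy effect, f = 0.5 | Overstatement, f = 0.5 |
|---|---|---|---|---|
| 5% | 0.247 L | 0.013 L (5.3%) | 0.254 L | 0.0065 L (2.6%) |
| 10% | 0.234 L | 0.026 L (11.1%) | 0.247 L | 0.013 L (5.3%) |
| 15% | 0.221 L | 0.039 L (17.6%) | 0.240 L | 0.0195 L (8.1%) |

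If m = 0 or f = 1 the overstatement is zero.

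**4. Does the SAP wording matter?** Take m = 10%, r = 5%, f = 0. The treatment-policy effect is 0.85 × 0.26 = 0.221 L. The protocol version gives 0.95 × 0.26 = 0.247 L (11.8% too high). The SAP version gives 0.221/0.90 = 0.246 L (11.1% too high). A large-sample sequential-regression fit stands in for an unstructured MMRM with monotone dropout. It assumed five visits, correlation 0.7, SD 0.35 L and dropout unrelated to outcome, and it gave 11.2%. With m = 20% and r = 10% the three figures are 28.6%, 25.0% and 25.4%. The wording changes little. What matters is that the model does not distinguish on-drug from off-drug visits.

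**5. Against the standard error.** If the true on-drug effect equals the blacked-out planning difference, D/SE = (D/SD)√(n/2). At 28 per arm this is 1.01 × √14 = 3.78, and it is almost the same at 27 and 26. The bias at f = 0 is m × 3.78, that is 0.19, 0.38 and 0.57 SE for 5, 10 and 15% missing. At f = 0.5 it is half of that.

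**6. Share missing versus share leaving.** Leavers are asked to attend an early termination visit with the end-of-study assessments, which include spirometry (protocol 9.1.2, Table 1). SAP 11.4 and Table 3 allow that visit to be mapped to Week 24 if it falls on days 121 to 197. So m is smaller than the share who leave. It consists mainly of patients who leave before about day 121 or who do not attend that visit.

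**The case against.** The strongest case on the other side has five parts.

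- A reader might infer that leavers are modelled as if still on drug and credited with the full on-drug benefit. The SAP does not say that. Its comparison group is everyone in the arm with a value, and observed off-drug values enter the model. This stands against the stronger reading, but step 4 shows that the lean remains.
- Full loss of benefit is a worst case. Protocol 3.2.1 bases the 12-week follow-up on the time for drug levels to fall below quantification, so a patient whose last dose came after about Week 12 may still have measurable drug at Week 24. This stands, and it is why the half-retained case is shown beside the full-loss case.
- Not everyone who leaves is missing at Week 24 (step 6), and patients who stop drug are encouraged to stay. This stands, subject to the conflict between protocol 8.4.2 and 8.4.2.2.
- The tipping point analysis already probes MAR, and it runs when a false positive is possible. If its shifts apply to dupilumab leavers, one of them may come close to a reference-based result. This stands in part. Its steps are not visible, so one cannot claim that it ignores the problem. The legible text does make it conditional on significance. A tipping point shows how far values must move to overturn a result, and it is not presented as an estimate under an off-drug assumption.
- Reference-based imputation does not identify the treatment-policy value either. Leavers may take other treatment, and the Amendment 3 rationale notes that dupilumab is authorized for asthma, which every patient has. This stands, and it limits how the added analysis may be described.

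**Conclusion.** The mismatch between the stated strategy and the handling of study leavers is real. The documents also word the MAR assumption in two ways. If dupilumab leavers lose some benefit, the estimate favours dupilumab. On the illustrative 0.26 L, the overstatement is about 5/11/18% for 5/10/15% missing at Week 24 with all benefit lost, and 3/5/8% with half kept.

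The actual size is unknown. The documents support neither a firm litre figure nor the inference that the primary test is invalid, because dropout, SD and planned difference are blacked out and 0.26 L is only a post-hoc subgroup result. The MMRM remains a reasonable primary analysis. What the plan lacks is an estimate under an off-drug assumption that is reported whether or not the primary result is significant. This is a cheap improvement, not a flaw that undermines the trial.

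**What to change.** - In SAP 7.2.1.2 add one pre-specified sensitivity analysis, run whatever the primary p-value. Use multiple imputation with the MMRM covariates. Impute intermittent gaps under MAR within arm, and impute dupilumab-arm values after study withdrawal from the placebo arm (jump- or copy-reference, chosen in advance). Combine by Rubin's rules and add the analysis to the SAP 14.1 table.
- Describe it as a conservative off-drug scenario, not as the true treatment-policy value.
- Keep the MMRM as primary and the tipping point analysis as planned.
- Align the MAR wording of protocol 11.4.3 with SAP 7.2.1.1. This removes the contradiction but on its own changes no result.
- Have the sponsor reconcile protocol 8.4.2 with 8.4.2.2 on whether patients who are off drug stay in the study.

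The cost is one SAP paragraph, one extra programmed analysis and a wording change. The downside is a sensitivity estimate that is likely to be somewhat less favourable than the MMRM.
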